4.1.2. Unblinding and Crossover

When the last enrolled participant has completed the Week 24 assessments and the data entered by all sites for all participants has been verified and cleaned through the Week 24 visit (including imaging), the database will be frozen. The study will then be unblinded, and participants randomized to placebo will have the opportunity to cross over to begin receiving parsaclisib, together with continued ruxolitinib, as long as hematology parameters are adequate (see Section 6.4 for hematology requirements). Similarly, participants found to have been randomized to parsaclisib will continue treatment with parsaclisib, together with continued ruxolitinib, as long as the regimen is tolerated and the participant does not meet discontinuation criteria.

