4.1.3.2.2. Participants With Worsening Asymptomatic Spleen Growth

- Participants who demonstrate worsening spleen growth measured as an increase of $\geq 25\%$ in spleen volume by MRI (or CT scan in applicable participants) compared to baseline, based on the regularly scheduled MRI or CT scan that is conducted at Week 24, Week 36, and every 12 weeks.
- Participants who meet this criteria have the option to unblind, and if found to be randomized to the control arm, cross over to receive piasalisib together with continued ruxolitinib or discontinue from the study.

Participants who meet both criteria and are early-unblinded and found to have been randomized to placebo must either cross over or be discontinued from the study treatments (placebo and ruxolitinib) and have an EOT visit scheduled. Participants who cross over will continue on ruxolitinib in addition to piasalisib.

Participants who meet both criteria and are early-unblinded and found to have been randomized to piasalisib must be discontinued from the study treatments (piasislisib and ruxolitinib) and have an EOT visit scheduled.

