6.4. Dose and Requirement to Start Dosing After Crossover

After criteria for crossover have been met (early or for entire study) and sites have received notification that unblinding and crossover may occur, the crossover visit will be scheduled and dosing with parsaclisib will begin as long as the following hematology criteria are met based on a laboratory visit within 2 weeks of the planned parsaclisib start date:

- The platelet count is at least $50 \times 10^9/L$.
- The ANC is at least $0.5 \times 10^9/L$.

No more than 3 repeat assessments for platelet count and ANC are allowed. Participants who have received 1 or more platelet transfusions must have a platelet count $\geq 50 \times 10^9/L$ at least 7 days after the most recent platelet transfusion to qualify for crossover. Participants in whom the platelet count and/or ANC remain below these thresholds at the time of the later of (a) 4 weeks or (b) the next regularly scheduled study visit following the date at which it was

determined that crossover could occur will be discontinued from the study and that visit will constitute the EOT.

The dose of piasalisib will be 5 mg QD, taken in the morning, without regard to food.

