6.7. Dose Modifications

6.7.1. Dose Increases for Inadequate Efficacy

6.7.1.1. Dose Increases for Piasalisib

The dose of piasalisib (or matching placebo) will be 5 mg QD. Dose increases are not allowed at any time during the study. If a dose has been reduced due to AEs, the dose may be increased back to the original starting dose of 5 mg QD once safety has adequately resolved (see Section 6.7.2).

6.7.1.2. Dose Increases for Ruxolitinib for Participants Entering the Study With a Platelet Count $\geq 100 \times 10^9/L$

The initial dose of ruxolitinib will be 15 mg BID. Dose increases are optional. After the first 4 weeks of therapy, doses may be increased by 5 mg BID for participants who demonstrate inadequate efficacy and who meet the following 3 conditions:

1. Inadequate efficacy is demonstrated by palpable spleen length below the costal margin that has been reduced by $< 50\%$ at the Week 4 visit relative to baseline.

2. Platelet count at the Week 4 blood draw is $> 125 \times 10^9/L$ and platelet count has never been $< 100 \times 10^9/L$ at a prior laboratory evaluation since baseline.
3. Absolute neutrophil count has remained $> 0.75 \times 10^9/L$ since baseline.

A second dose increase may be instituted at Week 8 if these 3 criteria are still met (reference point is 8 weeks).

No dose increases after Week 8 are allowed except dose increases related to a recovery from a prior dose reduction or hold.

A dose increase at Week 4 does not mean an automatic dose increase at Week 8. A dose not being increased at Week 4 because criteria were not met does not preclude a dose increase at Week 8 if criteria are met.

The dose of ruxolitinib may never exceed 25 mg BID.

6.7.1.3. Dose Increases for Ruxolitinib for Participants Entering the Study With a Platelet Count of 50 to $< 100 \times 10^9/L$ Inclusive

The initial dose of ruxolitinib will be 5 mg BID. Dose increases are optional.

Starting at the Week 4 visit, doses of ruxolitinib may be increased in 5 mg QD increments up to a dose of 10 mg BID. Dose increases may occur no more frequently than every 4 weeks and only if the following conditions are met:

- Platelet count was always $\geq 40 \times 10^9/L$ since the last scheduled study visit.
- Platelet count, if decreased since the last scheduled study visit, was decreased by no more than 20% of the platelet count at the last scheduled visit.
- No dose decreases or holds for safety occurred during the preceding 4-week interval.

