7.1.2. Discontinuation Procedures

The decision to discontinue study treatment and reference treatment will not constitute study withdrawal or study completion. In the event that the decision is made to discontinue study treatment and reference treatment, the treatment portion will be considered complete and the follow-up part of the study will begin.

If a participant is discontinued from study treatment:

- The study monitor or sponsor must be notified.
- The reason(s) for discontinuation must be documented in the participant's medical record and the primary reason for discontinuation must be included in the eCRF.
- The EOT visit should be performed and date recorded.
- The last date of the last dose of study drug/reference treatment will be recorded in the eCRF.
- The status of the participant should be updated to EOT in the IXRS.

- Participants must be followed for safety until the time of the follow-up visit or until study drug/reference treatment–related toxicities resolve, return to baseline, or are deemed irreversible, whichever is longest.
- Participants will be followed for subsequent MF treatment regimens and survival via periodic telephone contact. Results of these contacts will be recorded in the eCRF.

If the participant discontinues study treatment/reference treatment and actively withdraws consent for collection of follow-up data (safety follow-up or disease assessment), then no additional data collection should occur; however, participants will have the option of withdrawing consent for study treatment/reference treatment and further assessments but allowing survival follow-up.

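### Read literally, Protocol 6.4 ends survival follow-up for low-count placebo participants only, against 7.1.2 and 8.8.2; clarify before study-wide unblinding

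*Protocol*

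**What the plan says.** **The rule.** Protocol 6.4 applies to early and to study-wide crossover. To start parsaclisib, a participant needs platelets of at least 50 and ANC of at least 0.5 (×10⁹/L), with up to three repeat tests. Someone still below either count at the later of 4 weeks or the next scheduled visit falls under the sentence that ends "determined that crossover could occur will be discontinued from the study and that visit will constitute the EOT".

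**Whom it reaches.** Only controls can cross over. Section 4.1.2 says that "participants randomized to placebo will have the opportunity to cross over to begin receiving parsaclisib", on condition that the counts in 6.4 are met.

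**Similar wording elsewhere.** In 4.1.3.2.2 (asymptomatic spleen growth after Week 24), one bullet lets an unblinded control "cross over to receive piasalisib together with continued ruxolitinib or discontinue from the study". The closing paragraphs of that subsection, and 4.1.3.1 and 4.1.3.2.1, speak instead of stopping the study treatments and scheduling an EOT visit.

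**The general rule.** Section 7.1.2: "The decision to discontinue study treatment and reference treatment will not constitute study withdrawal or study completion". It then provides for telephone follow-up of survival. Section 8.8.2 starts survival follow-up at the last dose, with contact at least every 12 weeks, and ends it only at death, consent withdrawal or end of study. Table 2 says the same.

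**The endpoint.** OS is second in the fixed testing sequence (Protocol 10.3, SAP 3.2) and is tested at 85 deaths (Protocol 10.1). SAP 7.4.3 censors at the date last known alive.

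**The concern.** The protocol distinguishes stopping treatment from leaving the study, and 6.4 uses the second where the rest of the text implies the first. A site has two instructions that point opposite ways. If it follows 6.4, survival contacts stop for controls with persistently low counts, who plausibly have a worse prognosis. Nobody in the parsaclisib arm is exposed to this rule. The OS comparison would then lose deaths from one arm, selected by prognosis. The log-rank test assumes that censoring is uninformative. The planned rank-preserving structural failure time analysis is described as an adjustment for crossover, not for lost follow-up.

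A second inconsistency concerns treatment. It is not clear what should happen to a control, including background ruxolitinib, when parsaclisib cannot be started at study-wide crossover.

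**Working it through.** **1. Reproduce the OS design (Protocol 10.1).** Inputs: 440 randomized 1:1, 85 deaths, hazard ratio 0.54, 2-sided 5%, control median 5.3 years, accrual 1.5 years.

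- Schoenfeld events for 80% power: 4 × (1.960 + 0.842)² / (ln 0.54)² = 83.
- Power at 85 deaths: Φ(½ × √85 × |ln 0.54| − 1.960) = 81.1%.
- Deaths per arm by year T, with exponential survival and uniform accrual: 220 × [1 − (e^(−λ(T−1.5)) − e^(−λT)) / (1.5λ)]. Control λ = ln 2 / 5.3 = 0.1308; parsaclisib λ = 0.54 × 0.1308 = 0.0706.
- This reaches 85 deaths at 2.91 years and 88 at 3.0 years.

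The plan's 85 deaths, 80% power and 3 years are reproduced.

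**2. Deaths still to come at study-wide crossover.** The earliest date is 1.5 + 24/52 = 1.96 years; 2.1 years is assumed, to allow for data cleaning. By 2.1 years the formula gives 35.3 control and 19.9 parsaclisib deaths, 55.2 in all. About 85 − 55 = 30 remain, of which about 54 − 35 = 19 are in controls.

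**3. Effect of literal removal.** The documents do not give the share of participants below the counts or their excess hazard, so both are varied. Simulation: 2,500 trials per setting; the low-count subgroup is present in both arms; hazards are scaled to the 5.3-year control median. Low-count controls alive at 2.1 years are censored there. Analysis is at the 85th observed death, with unstratified log-rank and Cox. No crossover effect is modelled.

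| Low-count share | Relative hazard | Controls removed | Control deaths unseen | HR, kept → removed | Power, kept → removed |
|---|---|---|---|---|---|
| 5% | 2 | 7.9 | 1.5 | 0.539 → 0.545 | 79.6% → 78.0% |
| 5% | 4 | 5.8 | 1.8 | 0.540 → 0.561 | 78.8% → 74.6% |
| 10% | 2 | 15.8 | 3.0 | 0.537 → 0.552 | 79.5% → 77.0% |
| 10% | 4 | 12.0 | 3.5 | 0.550 → 0.578 | 77.0% → 70.0% |
| 20% | 2 | 32.7 | 6.2 | 0.540 → 0.571 | 79.1% → 72.0% |
| 20% | 4 | 26.3 | 6.7 | 0.561 → 0.608 | 74.1% → 61.8% |

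The hazard ratio moves toward 1 by 0.006 to 0.047, and power falls by 1.6 to 12.3 points.

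**4. Treatment rules side by side.**

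- *Platelets 40 to <50:* Tables 11 and 13 call for no interruption; 6.4 ends participation.
- *Platelets 25 to <40:* Table 11 interrupts parsaclisib/placebo only if this is a worsening grade from baseline. Table 13 adds ruxolitinib if the cytopenia persists.
- *Platelets <25 or ANC <0.5:* Table 11 interrupts whatever the baseline grade. Table 13 interrupts ruxolitinib if this persists beyond 14 days. Section 6.7.6 ends parsaclisib/placebo after a delay of more than 14 days unless the sponsor agrees to longer.
- *Mandatory reasons to stop (7.1.1):* missing the crossover counts is not listed.

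**The case against.** The strongest reply is that OS follow-up is already protected. The same sentence in 6.4 makes the visit the EOT, which 8.7 ties to stopping treatment, and 7.1.2 then starts the follow-up part of the study. Section 8.8.2 does not list missed counts among its end conditions. Section 4.1.3.2.2 uses both phrasings within one subsection, which suggests loose drafting. This largely stands: a reader might infer that the plan deliberately drops these controls from OS follow-up, and the documents do not support that. What remains is that 6.4, taken alone, tells a site to end participation.

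Other stronger readings also fail:

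- *Treatment would otherwise continue at every count that 6.4 excludes.* This is clear only at platelets 40 to <50. Tables 11 and 13 manage ongoing drug, whereas 6.4 governs starting one, with the same limits as exclusion criterion 5. Different limits for starting and continuing are not in themselves a contradiction.
- *Section 6.7.1.3 would even allow a ruxolitinib increase at platelets of 40 or more.* It covers only those who entered with platelets of 50 to <100, and it bars increases after Week 16 except on recovery from a reduction or hold. It does not describe participants at study-wide crossover.
- *Section 4.1.2 contradicts 6.4 on eligibility.* It does not: the opportunity to cross over is expressly conditional on 6.4. Only the consequence of missing the counts is unreconciled.
- *Only controls are ever made to stop treatment.* Participants unblinded early under the spleen-growth criteria and found to be on parsaclisib must stop both drugs. The one-arm feature is the removal from the study.

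The size is also open to challenge. It rests on assumed shares and hazards, on every affected control being lost, and on ignoring the planned crossover. A survival benefit after crossover would lower power before any removal and change the further loss, so the range illustrates sensitivity and is not a forecast.

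**Conclusion.** The contradiction is real and worth correcting. Sections 6.4 and one bullet of 4.1.3.2.2 conflict with 7.1.2, 8.8.2, Table 2 and the other wording in 4.1.3. If sites act on the literal text, OS is subject to informative censoring in the control arm only. Under the stated assumptions (5–20% at 2–4 times the hazard, all lost at about 2.1 years, no crossover effect), the cost is about 1.5–7 unseen control deaths, a shift of about 0.01–0.05 toward 1 and about 2–12 points of power. The likely direction is against parsaclisib, so it does not favour a false claim of benefit, but it would weaken a key secondary test.

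The primary analysis is not affected. For study-wide crossover, Week 24 data are complete before 6.4 applies. A control who stops treatment or crosses over before Week 24 is already a nonresponder under SAP 7.3.1. This is a clarification to make before study-wide unblinding, when most affected participants would leave.

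**What to change.** **Follow-up wording.** In 6.4 and 4.1.3.2.2, state that participants who miss the counts, or who do not cross over, are not withdrawn from the study and continue in safety and survival follow-up under 7.1.2 and 8.8.2. Do not simply import the phrase from 4.1.3.1: it names ruxolitinib among the drugs stopped and would settle a clinical question by drafting.

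**Treatment rule.** Separately, the clinical team must reconcile 6.4 with 4.1.2, 7.1.1 and Tables 11 and 13 on what happens to study treatment, including background ruxolitinib, when a control misses the counts at study-wide crossover. This review does not say which count or treatment rule is right.

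**Cost.** One sentence in two sections at the next amendment, plus a site memo. The 12-weekly survival contacts are already scheduled. The 85 deaths, the power and the timing stay as planned. It would also be sensible to check whether any early-crossover candidate has already been taken out of follow-up under 6.4.

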6.5. Study Treatment Compliance

Compliance with all study-related treatments should be emphasized to the participant by the site personnel, and appropriate steps should be taken to optimize compliance during the study.

Participants will complete daily dosing diaries (electronic or paper) and will bring them to each study visit. Compliance with piasalisib/matching placebo and with ruxolitinib administration will be calculated by the sponsor based on the drug accountability documented by the site staff and monitored by the sponsor/designee (tablet counts). Participants will be instructed to bring all unused study drug with them to the study visits in order for site personnel to conduct tablet counts to assess study drug accountability. The drug accountability documentation will be used by the sponsor to calculate treatment compliance.

6.6. Dose-Limiting Toxicity and Determination of Maximum Tolerated Dose and/or Pharmacologically Active Dose

Previously, the Phase 2 study INCB 50465-201 examined daily doses up to 20 mg for 8 weeks followed by doses up to 20 mg weekly or 5 mg daily. Pharmacological activity was observed at all dose combinations with 8 weeks of daily dosing followed by continued daily dosing or weekly dosing, although activity appeared to diminish with time with weekly dosing. Dose-limiting toxicities were not observed in any dosing part of the study, and the maximum tolerated dose was not reached.

6.7. Dose Modifications

6.7.1. Dose Increases for Inadequate Efficacy

6.7.1.1. Dose Increases for Piasalisib

The dose of piasalisib (or matching placebo) will be 5 mg QD. Dose increases are not allowed at any time during the study. If a dose has been reduced due to AEs, the dose may be increased back to the original starting dose of 5 mg QD once safety has adequately resolved (see Section 6.7.2).

6.7.1.2. Dose Increases for Ruxolitinib for Participants Entering the Study With a Platelet Count $\geq 100 \times 10^9/L$

The initial dose of ruxolitinib will be 15 mg BID. Dose increases are optional. After the first 4 weeks of therapy, doses may be increased by 5 mg BID for participants who demonstrate inadequate efficacy and who meet the following 3 conditions:

1. Inadequate efficacy is demonstrated by palpable spleen length below the costal margin that has been reduced by $< 50\%$ at the Week 4 visit relative to baseline.

2. Platelet count at the Week 4 blood draw is $> 125 \times 10^9/L$ and platelet count has never been $< 100 \times 10^9/L$ at a prior laboratory evaluation since baseline.
3. Absolute neutrophil count has remained $> 0.75 \times 10^9/L$ since baseline.

A second dose increase may be instituted at Week 8 if these 3 criteria are still met (reference point is 8 weeks).

No dose increases after Week 8 are allowed except dose increases related to a recovery from a prior dose reduction or hold.

A dose increase at Week 4 does not mean an automatic dose increase at Week 8. A dose not being increased at Week 4 because criteria were not met does not preclude a dose increase at Week 8 if criteria are met.

The dose of ruxolitinib may never exceed 25 mg BID.

6.7.1.3. Dose Increases for Ruxolitinib for Participants Entering the Study With a Platelet Count of 50 to $< 100 \times 10^9/L$ Inclusive

The initial dose of ruxolitinib will be 5 mg BID. Dose increases are optional.

Starting at the Week 4 visit, doses of ruxolitinib may be increased in 5 mg QD increments up to a dose of 10 mg BID. Dose increases may occur no more frequently than every 4 weeks and only if the following conditions are met:

- Platelet count was always $\geq 40 \times 10^9/L$ since the last scheduled study visit.
- Platelet count, if decreased since the last scheduled study visit, was decreased by no more than 20% of the platelet count at the last scheduled visit.
- No dose decreases or holds for safety occurred during the preceding 4-week interval.
- Absolute neutrophil count has been $> 1.0 \times 10^9/L$ since the last scheduled study visit.

Doses may not exceed 10 mg BID except in participants who continue to meet the above dose-escalation criteria [REDACTED]

[REDACTED] while receiving 10 mg BID. Such participants may continue dose escalation to a maximum dose of 15 mg BID. Note that when a 5 mg QD increment is added, creating a regimen such as 5 mg/10 mg, the higher dose should be taken in the evening and the lower dose in the morning.

Doses may never exceed 15 mg BID.

No dose increases after Week 16 are allowed except for dose increases related to a recovery from a prior dose reduction or hold.

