6.7.2. Dose Decreases of Parsaclisib/Placebo for Toxicity

Parsaclisib or matching placebo should be interrupted/decreased first, with no change to the ruxolitinib dosage. Adjustments to ruxolitinib may be utilized if interruption/dose adjustment of parsaclisib or matching placebo does not lead to resolution or at least improvement of the AE within a 14-day period (see Section 6.7.7). Treatment with parsaclisib or matching placebo may be delayed up to 2 weeks (14 days) to allow for resolution of toxicity. Participants may resume

treatment if no medical condition or other circumstance exists that, in the opinion of the investigator, would make the participant unsuitable for further participation in the study. The treating investigator should contact the sponsor to discuss the case of any participant whose treatment has been delayed for more than 14 days before restarting treatment with piasclisib or matching placebo and/or ruxolitinib. Adverse events that have a clear alternative explanation or transient (≤ 72 hours) abnormal laboratory values without associated clinically significant signs or symptoms may be exempt from dose-reduction rules.

Table 11 shows dose-reduction and interruption guidelines for piasclisib and matching placebo. Because participants may enter the study with extensive pretreatment and/or severe bone marrow infiltration by the primary disease, these dose-reduction rules are provided as guidelines (see **Table 11**). **Individual decisions regarding dose reduction/interruption should be made using investigator clinical judgment and in consultation with the sponsor's medical monitor in those cases where the guidelines will not be followed, taking into account relatedness of the AE to piasclisib and the participant's underlying condition.** Available dose strengths for piasclisib/matching placebo are shown in **Table 12**.

Table 11: Guidelines for Interruption and Restarting of Piasclisib/Matching Placebo

Adverse Event	Action Taken
Chemistry	

 • AST and/or ALT $> 5.0 \times$ ULN (Grade 3). 	
Step 1: Interrupt piasclisib or matching placebo for up to 2 weeks (14 days) until the toxicity has resolved to \leq Grade 1 except by approval of the medical monitor.
 
Step 2: Restart piasclisib or matching placebo at the same dose. If assessed as related to piasclisib or matching placebo, restart piasclisib or matching placebo at the next lower dose; monitor as clinically indicated.

Hematology	

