
 • ANC $< 1.0 \times 10^9/L$ (Grade 3) unless because of underlying disease. Applies only if this represents a worsening grade from baseline. • Platelet count $\geq 25 \times 10^9/L$ and $< 40 \times 10^9/L$. Applies only if this represents a worsening grade from baseline. 	
Step 1: Interrupt piasclisib or matching placebo for up to 2 weeks (14 days) until the toxicity has resolved to \leq Grade 1 or pretherapy baseline.
 
Step 2: Restart piasclisib or matching placebo at the same dose and monitor as clinically indicated.

 • Grade 4 ANC ($< 0.5 \times 10^9/L$) regardless of baseline grade. • \geq Grade 3 ANC with temperature of at least $38.5^\circ C$ OR with \geq Grade 3 infection regardless of baseline grade. • Platelet count is $< 25 \times 10^9/L$ (Grade 4), regardless of baseline grade. 	
Step 1: Interrupt piasclisib or matching placebo for up to 2 weeks (14 days) until the toxicity has resolved to \leq Grade 1 or pretherapy baseline.
 
Step 2: Restart piasclisib or matching placebo at the next lower dose; monitor as clinically indicated. Escalate to original dose with recovery to preinterruption levels of analyte.

Nonhematologic toxicities	

 • Diarrhea/colitis (Grade 1) 	
Step 1: Treat with antimotility agents (eg, loperamide) and initiate supportive care. If not improved after 48 hours, treat per guidance for Grade ≥ 2.

Table 11: Guidelines for Interruption and Restarting of Parsaclisib/Matching Placebo (Continued)

Adverse Event	Action Taken

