6.7.7. Dose Decreases of Ruxolitinib for Safety

Dose modifications/interruptions of ruxolitinib because of toxicity are not required unless piasclisib modifications/interruptions have been first implemented for 14 days with no improvement in toxicity grade. Doses of ruxolitinib may be modified/interrupted earlier if the study investigator deems this necessary. Dose interruptions and modifications for ruxolitinib because of hematologic toxicity that continues after interruption of INCB050465 are shown in [Table 13](#).

Table 13: Dose Reductions/Interruptions and Restarts for Hematologic Toxicities That Persist for > 14 Days After Interruption of Parsaclisib

ANC ($\times 10^9/L$)			Platelet Count ($\times 10^9/L$)		Dose of Ruxolitinib
Value	CTCAE Grade		Value	CTCAE Grade	
0.5 to < 1.0	3	or	25 to < 40	Below UL of Grade 3	If Grade 3 cytopenia persists for > 14 days after interrupting parsaclisib/matching placebo or if the primary investigator deems that earlier interruption of ruxolitinib is necessary , then ruxolitinib will be interrupted until the toxicity is resolved to \leq Grade 1 or pretherapy baseline and then restarted at the current dose. If a Grade 3 event recurs and persists for > 14 days after interrupting parsaclisib/matching placebo or if the primary investigator deems that earlier interruption of ruxolitinib is necessary, then ruxolitinib will be interrupted and the restart dose (after recovery to \leq Grade 1 or pretherapy baseline) of ruxolitinib will be 1 dose level (5 mg BID less) lower than the dose that resulted in the cytopenia. A participant who was taking 5 mg BID will restart at 5 mg QD.
< 0.5	4	or	< 25	4	If Grade 4 thrombocytopenia or neutropenia occurs and persists for > 14 days after interrupting parsaclisib/matching placebo or if the primary investigator deems that earlier interruption of ruxolitinib is necessary , then ruxolitinib will be interrupted until toxicity is resolved to \leq Grade 1 or pretherapy baseline and the restart dose will be 1 dose level (5 mg BID less) lower than the dose that resulted in the cytopenia. A participant who was taking 5 mg BID ruxolitinib will restart at 5 mg QD.

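### In the platelet ≥ 100 × 10⁹/L group, a new fall in ANC to between 0.75 and 1.0 × 10⁹/L leaves an optional ruxolitinib increase open under 6.7.1.2, while 6.7.2, Table 11 and Table 13 call for holding parsaclisib/placebo, leaving ruxolitinib unchanged and, if the fall persists, interrupting ruxolitinib

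*Protocol*

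**What the plan says.** Protocol 6.7.1.2 covers participants who enter with platelets ≥ 100 × 10⁹/L and start ruxolitinib at 15 mg BID. It allows, but does not require, an increase of 5 mg BID after the first 4 weeks and a second at Week 8, to a ceiling of 25 mg BID. Three conditions apply:

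- palpable spleen length has fallen by less than 50%;
- platelets exceed 125 × 10⁹/L and have not been below 100 × 10⁹/L since baseline;
- "Absolute neutrophil count has remained $> 0.75 \times 10^9/L$ since baseline".

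On toxicity, Table 11 in 6.7.2 interrupts parsaclisib/placebo for up to 14 days on this trigger: "ANC $< 1.0 \times 10^9/L$ (Grade 3) unless because of underlying disease. Applies only if this represents a worsening grade from baseline". The opening of 6.7.2 sets the order: "Parsaclisib or matching placebo should be interrupted/decreased first, with no change to the ruxolitinib dosage". Ruxolitinib may then be adjusted if the event has not improved within 14 days. Table 13 in 6.7.7 covers ANC of 0.5 to < 1.0 × 10⁹/L: "If Grade 3 cytopenia persists for > 14 days after interrupting parsaclisib/matching placebo", or sooner if the investigator thinks it necessary, ruxolitinib is interrupted.

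For participants entering with platelets of 50 to < 100 × 10⁹/L, 6.7.1.3 sets different conditions for an increase. They include "Absolute neutrophil count has been $> 1.0 \times 10^9/L$ since the last scheduled study visit" and "No dose decreases or holds for safety occurred during the preceding 4-week interval". Section 6.7.1.2 has no counterpart to the second of these, and its ANC limit is lower.

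**The concern.** The ANC limit for raising ruxolitinib in the higher-platelet group lies inside the range that the toxicity rules treat as Grade 3 neutropenia. Two sites with the same newly neutropenic participant could each follow the protocol and do different things: one raises ruxolitinib under 6.7.1.2, the other leaves it alone under 6.7.2 or interrupts it under Table 13.

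Section 2.6.2.1 names neutropenia among the effects seen with ruxolitinib in MF. Raising that drug while the other is on hold for neutropenia makes it harder to tell which drug is responsible and whether the hold is working. What is at stake is participant safety and uniform handling of the background drug.

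**Working it through.** No sample size, power or alpha is involved. The check compares the stated ANC ranges, the visit timing and the size of the dose step.

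**1. ANC ranges (× 10⁹/L)**

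| Source | Effect | ANC range |
|---|---|---|
| 6.7.1.2, condition 3 | ruxolitinib may be increased | > 0.75 |
| Table 11, ANC row | interrupt parsaclisib/placebo (worsening grade, not underlying disease) | < 1.0 |
| Table 13, Grade 3 row | interrupt ruxolitinib if it persists > 14 days after that hold | 0.5 to < 1.0 |
| 6.7.1.3 | ruxolitinib may be increased (50 to < 100 group) | > 1.0 |

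The first three rows intersect at 0.75 < ANC < 1.0, the upper half of the Grade 3 band. The 6.7.1.3 limit does not intersect the interruption range, so the overlap is confined to the ≥ 100 group.

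**2. Who is affected.** Exclusion criterion 5b excludes only ANC < 0.5, so a participant may enter at 0.5 to < 1.0. That participant is already Grade 3, and a later value between 0.75 and 1.0 is not a worsening grade, so this Table 11 row does not apply. The overlap therefore concerns participants with baseline ANC ≥ 1.0 who fall into the band for a reason other than underlying disease.

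**3. Can the rules meet at one visit?** Table 5 schedules hematology at Weeks 2, 4, 6 and 8. Under Tables 3 and 5 the windows are ± 3 days at Weeks 2 and 6 and ± 5 days at Weeks 4 and 8. The Week 2 to Week 4 gap is nominally 14 days and can range from 14 − 3 − 5 = 6 days to 14 + 3 + 5 = 22 days. The same holds for Week 6 to Week 8. A hold started at the Week 2 or Week 6 draw can therefore have lasted more than 14 days when the increase is decided. On the exact nominal schedule it would have lasted 14 days, which is not more than 14, so the collision is possible but not automatic.

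**4. Worked case.** Baseline ANC 2.0; ANC 0.85 at Week 2, and parsaclisib/placebo is held that day. The Week 4 visit falls more than 14 days later: ANC still 0.85, platelets 150 and never below 100, spleen length down 30%.

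- 6.7.1.2: all three conditions are met, so ruxolitinib may rise by 5 mg BID.
- Table 13: Grade 3 neutropenia has lasted more than 14 days after the hold, so ruxolitinib is interrupted.

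If the 0.85 is first seen at Week 4, the conflict is milder. 6.7.1.2 permits the increase, while Table 11 holds parsaclisib/placebo and 6.7.2 leaves ruxolitinib unchanged.

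**5. Size of a step.** 15 to 20 mg BID: 5/15 = +33%. 20 to 25 mg BID: 5/20 = +25%.

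**The case against.** The strongest reply is that an optional increase cannot contradict an instruction. A site that holds parsaclisib/placebo and leaves ruxolitinib alone, then interrupts it if the neutropenia persists, complies with every section. Table 11 is also expressly a guideline. It exempts transient values (≤ 72 hours) without clinically significant signs or symptoms, and events with a clear alternative explanation. Appendix J records that the 6.7.1.2 rules were changed deliberately in Amendment 1 to follow US labeling more closely, so a difference between platelet groups is not in itself an error.

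All of this narrows the point. It does not remove it, because a site that does raise ruxolitinib also has a section to cite and nothing gives 6.7.2 or Table 13 precedence. Departing from the Table 11 guidelines calls for consultation with the medical monitor, but 6.7.1.2 has no such step.

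A second reply is that 6.7.2 already settles the matter. If its sentence about leaving ruxolitinib unchanged covers efficacy increases, escalation is barred during any parsaclisib/placebo hold. If it covers only decreases, as the section heading suggests, it does not contradict 6.7.1.2. Both readings are open, and this ambiguity is part of what needs fixing. Even the second leaves the collision with Table 13.

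A reader might also infer more than the documents support:

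- **That any ANC in the band creates the conflict.** The worsening-grade and underlying-disease limits rule this out.
- **That ruxolitinib could rise by 67% during a hold.** That figure (25/15) is the cumulative ceiling after two steps. The decisions are 28 days apart, holds are nominally up to 14 days, and persistent neutropenia would trigger Table 13 in between.
- **That 6.7.1.2 clearly allows increases during a hold for any other toxicity.** 6.7.2 can be read as barring them.
- **That 6.7.1.3 bars an increase after a parsaclisib/placebo hold.** Its bullet does not name the drug and sits in a list about ruxolitinib doses.
- **That the Week 12 or Week 24 results are compromised.** The documents give no frequency, and investigators are blinded to arm when they decide.

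**Conclusion.** The inconsistency stands in a limited form. It applies to participants in the ≥ 100 × 10⁹/L platelet group with baseline ANC ≥ 1.0 × 10⁹/L who fall to 0.75 < ANC < 1.0, not because of underlying disease, and who also meet the spleen and platelet conditions at Week 4 or Week 8. When the fall has lasted more than 14 days after the parsaclisib/placebo hold, the same visit can carry permission to raise ruxolitinib and an instruction to interrupt it.

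The discrepancy is one 5 mg BID step (+33% or +25%). The number of participants affected cannot be estimated from the documents. The conclusion rests on the Table 11 guideline being followed and on no unstated rule of precedence. It should be corrected for safety and uniform site conduct; it is not a demonstrated threat to the primary analysis.

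**What to change.** Reconcile condition 3 of 6.7.1.2 with the Table 11 ANC row, the opening sentence of 6.7.2 and Table 13, and state which passage governs when they meet. In the same text, clarify two things:

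- whether the instruction in 6.7.2 to leave ruxolitinib unchanged covers efficacy increases under 6.7.1.2 while parsaclisib/placebo is on hold;
- which drug's decreases and holds the 6.7.1.3 bullet refers to.

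The threshold and the rule are for the clinical team to decide; this review takes no position on either. The cost is one or two sentences in an amendment or clarification letter, and a few optional increases may not happen.
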